9.2.8 Potential Drug-induced Liver Injury

Wherever possible, timely confirmation of initial liver-related laboratory abnormalities should occur prior to the reporting of a potential drug-induced liver injury (DILI) event. All occurrences of potential DILIs meeting the defined criteria must be reported as SAEs (see Section 9.2.5 and Appendix 3 for reporting details).

Potential DILI is defined as:

• Aminotransferase (AT; ALT or AST) elevation > 3 times ULN,

AND

• Total bilirubin > 2 times ULN, without initial findings of cholestasis (elevated serum alkaline phosphatase),

AND

• No other immediately apparent possible causes of AT elevation and hyperbilirubinemia, including, but not limited to, viral hepatitis, pre-existing chronic or acute liver disease, or the administration of other drug(s) known to be hepatotoxic.

9.2.9 Other Safety Considerations

Any significant worsening noted during interim or final physical examinations, electrocardiogram (ECG), X-ray filming, any other potential safety assessment required or not required by the protocol should also be recorded as a non-serious or serious AE, as appropriate, and reported accordingly.

9.3 Overdose

In the event of an overdose, the investigator should:

- Contact the Medical Monitor immediately.
- Closely monitor the participant for AEs/SAEs and laboratory abnormalities.

Decisions regarding dose interruptions will be made by the investigator in consultation with the Medical Monitor based on the clinical evaluation of the participant.

9.4 Safety

Planned time points for all safety assessments are listed in the Schedule of Activities (Section 2).

9.4.1 Physical Examinations

Refer to Schedule of Activities (Section 2). A complete physical examination will include general appearance, eyes, ears, nose, mouth, throat, neck, respiratory, cardiovascular, gastrointestinal/abdomen, lymphatic, musculoskeletal, skin, psychiatric, and neurologic exams. A targeted physical examination will include any organ system associated with an AE or a laboratory abnormality.

9.4.2 Vital Signs

Vital signs include body temperature, respiratory rate, and seated blood pressure and heart rate. Refer to Schedule of Activities (Section 2).

9.4.3 Electrocardiograms

Refer to Schedule of Activities (Section 2). A 12-lead ECG will be performed at the visits indicated in the Schedule of Activities. The participant must have his or her lab work done after the ECG tracing so that the ECG results remain as accurate as possible. The ECG results will be read by the primary study investigator or a designee.

9.4.4 Clinical Safety Laboratory Assessments

Investigators must document their review of each laboratory safety report.

A central/local laboratory will perform the analyses and will provide reference ranges for these tests.

Hematology				
Complete blood count:				
Hemoglobin				
Iematocrit				
Total leukocyte count, including differential				
Platelet count				
Chemistry				
Aspartate aminotransferase (AST)	Total protein			
Alanine aminotransferase (ALT)	Albumin			
Total bilirubin	Sodium			
Direct bilirubin	Potassium			
Alkaline phosphatase	Chloride			
Lactate dehydrogenase (LDH)	Calcium			
Creatinine	Phosphorus			
Blood urea nitrogen (BUN)	Magnesium			
Uric acid	Creatine kinase			
Glucose ^a	Creatinine clearance (CLcr)- screening only			
Lipid Panel (Fasting)	·			
Cholesterol (total)				
High-density lipoprotein (HDL)				
Low-density lipoprotein (LDL)				
Triglycerides				

Protein Glucose Blood Leukocyte esterase Specific gravity pH Microscopic examination of the sediment if blood, protein, or leukocytes esterase are positive on the dipstick Serology Hepatitis C antibody confirmed by HCV-ribonucleic acid (RNA) testing if required Hepatitis B surface antigen (HBsAg) Hepatitis B surface antibody (HBsAb) Hepatitis B core antibody (HBcAb) HBV DNA as required with confirmed HBV infection; see Appendix 22 HIV antibody (screening only)

Hemoglobin A1c

Thyroid-stimulating hormone (TSH)

Abbreviations: ALT, alanine aminotransferase; AST, aspartate aminotransferase; BUN, blood urea nitrogen; CLcr, creatinine clearance; DNA, deoxyribonucleic acid; HBcAb, hepatitis B core antibody; HBsAb, hepatitis B surface antibody; HBsAg, hepatitis B surface antigen; HBV, hepatitis B virus; HCV, hepatitis C virus; HDL, high-density lipoprotein; HIV, human immunodeficiency virus; LDH, lactate dehydrogenase; LDL, low-density lipoprotein; RNA, ribonucleic acid; TSH, thyroid-stimulating hormone;

9.4.5 Estimated Glomerular Filtration Rate

Glomerular filtration rate will be estimated using the Modification of Diet in Renal Disease (MDRD) equation at Screening and during the study at select visits.

The MDRD equation is as follows:

eGFR = 175 × standardized serum creatinine $(SCr)^{-1.154}$ × age $^{-0.203}$ × 1.212 (if Black) or 0.742 (if female)

Note: GFR is expressed as mL/min/1.73 m² of BSA and SCr is expressed in mg/dL.

Participants with an eGFR < 45 mL/min will be excluded from participation.

Protocol Amendment No.: 02 Date:06-May-2024 IM011054

Deucravacitinib

[figure not shown]
^a Fasting glucose will be collected at time points indicated in the Schedule of Activities; non-fasting glucose will be collected at all other time points.

9.4.6 Tuberculosis Testing

9.4.6.1 Tuberculosis Screening and Chest Imaging

Chest imaging results and physical examinations are part of the process to assess a participant's eligibility, as outlined in Section 2 and as defined in exclusion criterion 4c, Section 6.2. Chest imaging (eg, chest X-ray, chest computed tomography scan) at the Screening Visit is required if not already performed and documented within 6 months of Screening Visit. A participant must not have active signs or symptoms of TB, as judged by the investigator, to be eligible for the study.

In addition to a complete physical examination and medical history to evaluate exposure to TB, all participants will have a screening test, an IGRA (eg, QuantiFERON®-TB Gold), performed centrally. If unable to obtain central laboratory results, an IGRA test could be obtained locally, after consultation with the Medical Monitor. A participant with an indeterminate IGRA test result must be re-tested for confirmation. If the second result is again indeterminate, the participant will be excluded from the study. If the second result is positive, the participant should be considered as having LTBI provided there are no signs or symptoms of active TB. If the second result is negative, the participant may be eligible provided no other exclusion criterion for TB is met.

[figure not shown]

[figure not shown]
9.4.8 Imaging Safety Assessment

[figure not shown]
Any incidental findings of potential clinical relevance that are not directly associated with the objectives of the protocol should be evaluated and handled by the primary study investigator as per standard medical/clinical judgment.

[figure not shown]
9.4.9 Unscheduled Safety Visits

[figure not shown]
The protocol does not mandate specific investigations at unscheduled visits. Unscheduled visit study procedures should be based on the clinical judgment of the investigator.

10 STATISTICAL CONSIDERATIONS

10.1 Sample Size Determination

A total sample size of approximately 650 participants randomized in a 1:1 ratio in a blinded fashion (approximately 325 participants each randomized to 6 mg deucravacitinib QD arm and placebo) will provide > 99% power to detect a 20% treatment difference between 6 mg deucravacitinib QD and placebo at Week 16 for ACR 20 response assuming a response of 55% for 6 mg deucravacitinib QD and of 35% for placebo (2-sided alpha = 0.05, chi-square test).

The sample size of 325 participants treated with 6 mg deucravacitinib QD in this study (IM011054) was also chosen to provide, along with participants from other Phase 3 PsA studies with

deucravacitinib, an adequate number of participants for the overall safety database for the PsA program.

In addition, this sample size will also provide enough power for all key secondary endpoints (that are tested in a testing strategy to control Type I error) as given in Table 10.3.1-1.

10.2 Populations for Analyses

For purposes of analysis, the following populations are defined:

Population	Description	
Enrolled	All participants who sign informed consent	
All Randomized	All randomized participants. Following the intent-to-treat principle, participants will be analyzed according to the treatment assigned at randomization. The efficacy analysis population will be the All Randomized Population.	
All Treated	All participants who were randomized and took at least 1 dose of investigational product. Data in this data set will be analyzed based on randomized treatment, except in the following cases:	
	• If a participant received the same incorrect treatment throughout the study, then the participant will be analyzed based on the treatment received.	
	• If a participant received IP from more than 1 treatment group, and none of the administrations were consistent with the assigned randomized treatment group, then the participant will be analyzed based on the first treatment received.	
	The safety analysis population will be the All Treated Population.	

10.3 Statistical Analyses

will describe the selection of participants to be included in the analyses and procedures for accounting for missing, unused, and spurious data. Below is a summary of planned statistical analyses of the primary and secondary endpoints.

A description of the participant population will be included in a statistical output report, including subgroups of age, gender, and race.

Week 52 analyses will be conducted after the Week 56 database lock and will include an assessment of safety and efficacy at all available time points

10.3.1 Efficacy Analyses

Endpoint	Statistical Analysis Methods
Primary	The primary efficacy analysis model for the primary endpoint, ACR 20 response at Week 16 (responder/non-responder), will use a Cochran-Mantel-Haenszel test
	to compare the response rates of 6 mg deucravacitinib QD to placebo. The risk difference and odds ratio and the corresponding 2-sided 95% confidence interval will be provided.
	Non-responder imputation will be used at Week 16 for participants who have a missing ACR 20 response at Week 16 or who discontinued treatment (for any reason) prior to Week 16. The same imputation will be used for the analysis of this outcome at other time points.
	The primary estimand for the primary endpoint, ACR 20 response at Week 16, will be the treatment difference between deucravacitinib 6 mg QD and placebo in ACR 20 response at Week 16 for all randomized participants. The occurrence of the intercurrent event of study treatment discontinuation (for any reason) prior to Week 16 or a missing ACR 20 response at Week 16 will be considered as a measure of nonresponse to treatment at Week 16 if the participant would have continued on the study treatment up to Week 16. Non-responder imputation will be used for the above intercurrent event. Study treatment discontinuation is the only intercurrent event that will be accounted for in the primary estimand and a composite variable strategy is applied.
	Two sensitivity analyses using different imputation methods will be conducted for the primary endpoint at Week 16 to examine the impact of missing data.
	 A multiple imputation (MI) approach A tipping point approach
	A supportive analysis will be provided for the primary endpoint at Week 16, including all available efficacy measurement for all randomized participants. These available data will include efficacy measurements observed after study treatment discontinuation and efficacy measurements observed after switch to other treatments.
	Details will be given in the SAP.

Endpoint	Statistical Analysis Methods
Secondary	Binary Endpoints:
	Binary endpoints (other than ACR 20 response at Week 16) up to Week 16 will be analyzed using the same method as for the primary endpoint.
	Continuous Endpoints (except structural damage):
	Change from baseline at Week 16 will be analyzed using an analysis of covariance (ANCOVA) model. The model will include treatment, randomization stratification variables, and baseline value.
	The primary estimand at Week 16 will be the treatment difference between deucravacitinib 6 mg QD and placebo for changes from baseline at Week 16 for all randomized participants.
	In case an intercurrent event of study treatment discontinuation (for any reason) prior to Week 16 occurs, the efficacy assessments after the discontinuation of treatment will be considered missing. Missing values will be imputed with MI method assuming missing not at random (MNAR). The MNAR imputation assumes that after discontinuation of treatment, participants from the deucravacitinib 6 mg QD group (if they would have continued deucravacitinib 6 mg QD) exhibit a similar future evolution as participants from the placebo group. Study treatment discontinuation is the only intercurrent event that will be accounted for in the primary estimand and a composite variable strategy is applied.
	Structural Damage:
	Change from baseline in PsA-modified SvdH score (structural damage) at Week 16 will be analyzed using an ANCOVA model. The model will include treatment, randomization stratification variables, and baseline value.
	The primary estimand at Week 16 will be the treatment difference between deucravacitinib 6 mg QD and placebo for changes from baseline in PsA-modified SvdH score at Week 16 for all randomized participants based on all available data at Week 16, including those collected after study treatment discontinuation. Missing values at Week 16 will be imputed with MI method assuming MNAR. A treatment policy strategy is applied.
	Details will be provided in the SAP.

Multiplicity

In order to control the overall Type I error rate at 5%, a testing strategy for the primary and key secondary endpoints will be implemented. The primary endpoint, ACR 20 response at Week 16, will be tested at an alpha = 0.05. If the primary endpoint is significant at alpha = 0.05, then a testing strategy for the key secondary endpoints will be applied to control for the overall Type I error of 5%. The details about the full testing strategy including any hierarchy of key secondary endpoints will be provided

For the analysis of the key secondary endpoints, enthesitis and dactylitis, the data will be pooled for the studies IM011054 and IM011055.

The key secondary endpoints displayed in Table 10.3.1-1 will be included in a testing strategy to control for multiplicity to protect the overall 2-sided Type I error. Additional endpoints may also be included in the testing strategy (eg, ACR 50 and ACR 70) and will be detailed in the SAP. The power for those key secondary endpoints for a sample size of 325 participants each randomized to placebo and 6 mg deucravacitinib QD is given in Table 10.3.1-1.

Table 10.3.1-1: Power

Key Secondary Endpoint (Week 16)	Assumption - Treatment Effect	Power (with Nominal 2-sided Alpha = 0.05)
HAQ-DI		
PASI 75		
Enthesitis resolution		
Dactylitis resolution		
SF-36 PCS		
MDA		
FACIT-Fatigue		

der Heijde.

Table 1	0.3	.1-1:	Power
---------	-----	-------	-------

Structural progression (PsA-modified SvdH)	
DAS28-CRP	

Note: Chi-square test applied for binary variables, 2-groups t-test for continuous variables, alpha = 5% (2-sided).

Abbreviations:

DAS28-CRP, Disease Activity Score 28 with C-reactive protein; FACIT, Functional Assessment of Chronic Illness Therapy; HAQ-DI, Health Assessment Questionnaire - Disability Index; MDA, minimal disease activity; PASI, Psoriatic Area and Severity Index; PCS, Physical Component Summary; PsA, psoriatic arthritis;

SF-36, Short Form-36; SvdH, Sharp-van

The treatment estimates are based on results from the deucravacitinib Phase 2 study IM011084 and on results of golimumab, guselkumab, secukinumab, ixekizumab, upadacitinib (for modified total Sharp score). 51,52,53,54,55

Further details will be provided in the SAP.

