- i) Participant has received phototherapy (including either oral or topical psoralen ultraviolet A light therapy, ultraviolet B, or self-treatment with tanning beds, or therapeutic sunbathing) within 28 days prior to Day 1.
- j) Participant has used topical medications/treatments that could affect PsO evaluation, including, but not limited to, medium- or high-potency glucocorticoids (WHO Classes I through V), anthralin, calcipotriene, topical vitamin D derivatives, retinoids, tazarotene, methoxsalen, trimethylpsoralen, picrolimus, and tacrolimus, within 14 days of Day 1.

- k) Participant has used shampoos that contain glucocorticoids, coal tar, or vitamin D3 analogues within 14 days prior to Day 1.
- 1) Participant who has received any experimental therapy or new investigational agent, including those for SARS-CoV-2, may not participate in the study until the protocol-specific washout period is achieved (4 weeks or 5 half-lives, whichever is longer) prior to Day 1 or is currently enrolled in an investigational study.
 - Note: As outlined in exclusion criterion 3), if a study participant has received an investigational SARS-CoV-2 vaccine prior to Screening, enrollment should be delayed until the biologic impact of the vaccine is stabilized, as determined by discussion between the investigator and the Bristol-Myers Squibb Company (BMS) Medical Monitor.
- m) Participant has had any major surgery within 8 weeks prior to Day 1, or any planned surgery for the first 52 weeks of the study.
- n) Participant has donated blood > 500 mL within 28 days prior to Day 1, or intends to donate blood during the course of the study.
- o) Participant has abused drugs or alcohol, as determined by the investigator, within 6 months prior to Day 1.
- p) Participant has had any major illness/condition or evidence of an unstable clinical condition (eg, renal, hepatic, hematologic, gastrointestinal, endocrine, pulmonary, psychiatric, immunologic, or local active infection/infectious illness) that, in the investigator's judgment or after consultation with the Medical Monitor, will substantially increase the risk to the participant if he or she participates in the study.
- q) Participant has had unstable cardiovascular disease, defined as a recent clinical deterioration (eg, unstable angina, myocardial infarction, stroke, rapid atrial fibrillation) in the last 6 months prior to Screening, or a cardiac hospitalization within the 6 months prior to Screening.

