7.7.3.1 Prohibited Treatments

• Use of opioid analysesics, if the average daily dose is > 30 mg/day of morphine or its equivalent (see Section 6.2), unless it is considered necessary for the participant's welfare and/or treatment of an AE/SAE.

- Phototherapy: use of tanning booths or therapeutic sunbathing are prohibited up to Week 52.
- Any use of the following oral PsO medications: cyclosporine, retinoids, fumaric acid derivatives are prohibited up to Week 52.
- High-potency glucocorticoids (WHO Classes I through V), > 3% salicylic acid, urea, alpha or beta hydroxy acids, anthralin, calcipotriene, vitamin D derivatives (oral vitamin D supplements are permitted), retinoids, tazarotene. Any medicated shampoos that contain glucocorticoids, coal tar, > 3% salicylic acid, or vitamin D3 analogues up to Week 52.
- Live vaccination, including live SARS-CoV-2 vaccines, during the study or within 60 days after completing study treatment (Section 6.2).
- Immune-suppressing immunomodulatory agents such as tacrolimus, sirolimus, mycophenolate mofetil, JAK inhibitors, and immunosuppressant biologic agents, including, but not limited to, TNF antagonists, anti-IL-17, anti-IL-12/23, anti-IL-23, and abatacept.

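### Can the PASI 75 result be trusted when no described analysis isolates prohibited skin therapy used by participants who stay on study drug?

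*Combined protocol and SAP*

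**What the plan says.** In the primary row of the efficacy table in Section 10.3.1, the only intercurrent event is stopping study treatment, and those who stop count as non-responders: "Study treatment discontinuation is the only intercurrent event that will be accounted for in the primary estimand and a composite variable strategy is applied". Binary endpoints other than ACR 20 "up to Week 16 will be analyzed using the same method as for the primary endpoint", which brings in PASI 75.

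The robustness work is attached to ACR 20. "Two sensitivity analyses using different imputation methods will be conducted for the primary endpoint at Week 16 to examine the impact of missing data"; these are multiple imputation and a tipping point. Then: "A supportive analysis will be provided for the primary endpoint at Week 16, including all available efficacy measurement for all randomized participants". That supportive analysis brings in data collected after stopping or switching.

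On skin therapy, Section 6.2 (criterion 2j) excludes on the ground "Participant has used topical medications/treatments that could affect PsO evaluation" within 14 days of Day 1, and criterion 2i excludes where "Participant has received phototherapy" within 28 days. Section 7.7.3.1 carries the restrictions into the study. It lists topical agents, medicated shampoos and oral psoriasis drugs, and adds: "Phototherapy: use of tanning booths or therapeutic sunbathing are prohibited up to Week 52". Section 8.1 requires study drug to stop for use of a biologic, JAK inhibitor or phosphodiesterase 4 inhibitor, for clinically significant worsening that needs medication outside the permitted list, and for non-compliance as judged by the investigator.

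**The concern.** Criterion 2j shows that the sponsor regards certain topicals as able to change a psoriasis assessment. Several of them (the listed glucocorticoids, anthralin, calcipotriene, retinoids, tazarotene) are also prohibited during the study. Yet the visible part of Section 8.1 does not make use of a prohibited topical, shampoo or phototherapy an automatic reason to stop. A participant could use one, stay on study drug and be counted as a PASI 75 responder. Because the non-compliance route is a judgement, two sites could treat the same behaviour differently.

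The described sensitivity analyses do not reach this case. They concern missing ACR 20 data, and the supportive analysis does not count users of other therapy as failures. PASI 75 is a key secondary endpoint under multiplicity control. If use were frequent and unequal between arms, part of the reported difference could reflect that therapy, and a reader could not tell how much.

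**Working it through.** **Inputs.** From Section 10.1: 325 per arm, ACR 20 rates of 55% and 35%, two-sided alpha 0.05. From Section 3.1: Phase 2 PASI 75 rates of 42.4% (6 mg) and 20.4% (placebo), used because the PASI 75 entries in Table 10.3.1-1 are not visible. From Table 4-1: PASI 75 is assessed in participants with BSA of at least 3% and sPGA of at least 2. *Assumed, because the documents give nothing:* a PASI set of 40% to 80% of each arm (130 to 260), prohibited use of 2% to 10%, and a response rate of 35% to 50% among users.

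**1. The plan's own figure.** With pooled variance under the null:
- SE0 = √(2 × 0.45 × 0.55 / 325) = 0.0390
- SE1 = √((0.55 × 0.45 + 0.35 × 0.65) / 325) = 0.0382
- z = (0.20 − 1.96 × 0.0390) / 0.0382 = 3.23, so power is 99.94%

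The stated figure of more than 99% is confirmed.

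**2. Who is left uncovered.** Worsening that needs non-permitted medication leads to stopping study drug (Section 8.1), and stopping leads to non-response (Section 10.3.1). Non-compliance as judged by the investigator follows the same path. Section 6.2 (criterion 7c) excludes people unable to keep to the prohibited-treatment rules, and Section 9 allows no waivers. What remains is use that is not a response to clinically significant worsening and that the investigator does not judge to be non-compliance. Section 7.3.1 keeps sites and participants blinded, so differences between sites in that judgement are not expected to follow treatment arm.

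**3. Effect on PASI 75 of counting those users as failures.** Let u be the proportion of users and r their response rate, with subscripts a (drug) and p (placebo):

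new difference = (0.424 − u_a r_a) − (0.204 − u_p r_p)

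With equal use u this is 0.220 − u(r_a − r_p). Since |r_a − r_p| ≤ 0.15, the shift is at most 0.15u.

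| Use | Range of difference (points) |
|---|---|
| 2% in both arms | 21.7 to 22.3 |
| 5% in both arms | 21.25 to 22.75 |
| 10% in both arms | 20.5 to 23.5 |
| 10% drug, 2% placebo (lowest) | 22.0 − 5.0 + 0.7 = 17.7 |
| 2% drug, 10% placebo (highest) | 22.0 − 0.7 + 5.0 = 26.3 |

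Where use is commoner on placebo, the planned rule understates the drug effect.

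**4. Distance from losing significance.** Drug-arm responders are reclassified one at a time, with no placebo responder reclassified, until the uncorrected chi-square test gives p of 0.05 or more.

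| PASI set per arm | Responders, drug vs placebo | Reclassified | Share of drug responders |
|---|---|---|---|
| 130 | 55 vs 27 | 15 | 15/55 = 27% |
| 195 | 83 vs 40 | 27 | 27/83 = 33% |
| 260 | 110 vs 53 | 38 | 38/110 = 35% |

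Check at 130: 40 vs 27 gives a difference of 0.100, SE √(0.2577 × 0.7423 × 2/130) = 0.0542 and z = 1.84, which is below 1.96. With 14 reclassified (41 vs 27), z = 1.98.

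**5. ACR 20.** With 0% to 2% use and the same user response rates, the difference lies between 20 − 0.02 × 50 = 19.0 and 20 + 0.02 × 50 = 21.0 points. Power at 54% vs 35% is 99.85%. Reaching p = 0.05 would take 41 of 179 drug responders (23%).

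**The case for a change.** The best opposing case is that the described analyses do leave this question untested. Extending all three ACR 20 analyses to PASI 75 would not help, since none addresses observed responses in people still on drug. Strongly one-sided use would matter: if 20% of drug-arm responders were users and no placebo responder was, the difference would fall to 0.424 × 0.80 − 0.204 = 13.5 points, and power with 130 per arm would drop from 97.2% to 69.0%. Data capture is also a fair question. Section 7.7 names systemic medications for PsA and psoriasis, while current topicals are mentioned only in the screening table.

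The first point stands as a description of the available text. However, Section 10.3 presents itself as a summary and defers details to the SAP. No SAP text was available for this check, and parts of Sections 7.7, 8.1 and 10.3 are blacked out, so absence here does not show absence from the plan. The 13.5-point case is pure assumption: it requires one drug responder in five to be a user and no reclassification on placebo. Even then the result stays significant, since 20% of 55 is 11, below the 15 needed. On data capture, Tables 2-2 and 2-3 record concomitant medication at every visit, and Section 7.7 does not restrict that record to systemic drugs. That is a query for the CRF instructions and does not show an error.

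The choice of endpoints for an added analysis is also a matter of preference. ACR 20 is barely exposed, whereas MDA has an explicit PASI or BSA component, so the documents do not mark out PASI 75 and ACR 20 as the pair that must be tested.

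**Conclusion.** The concern does not hold. The plan has a defined rule for these participants (observed scoring while on study drug), and that rule is a legitimate primary choice. The clinically important routes to other therapy already end in non-response through Section 8.1. Neither the size nor the direction of any distortion can be derived from the documents. Under the assumptions used here (2% to 10% use, 35% to 50% response among users, a PASI set of 40% to 80%, Phase 2 rates), equal use shifts PASI 75 by no more than 1.5 points. Sharply unequal use shifts it by 4.3 points either way, and the conclusion on significance is robust. A tabulation of prohibited use by arm, or an analysis without alpha that counts users as failures, would be informative but optional. Leaving it out does not undermine the result.
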